Limb salvage rates are thought to be similar with both endovascular and open techniques, however the data are limited and there is a large ongoing randomized controlled trial addressing this issue (Adam et al., 2005; Albers, Romiti, Brochado-Neto, De Luccia, & Pereira, 2006; Romiti et al., 2008). Endovascular techniques offer a less invasive option with typically only one or two small (≤ 5 mm) groin incisions to access the affected vessels. It also has an advantage of lower morbidity and with open bypass procedures (Adam et al., 2005). Endovascular options typically require iodinated contrast, which may expose the patients to a risk of kidney injury, which is not uncommon in this population given their comorbidities, and in particular a high frequency of diabetes. While open bypass procedures may be associated with higher wound complication rates, they have been shown to have better long-term patency compared with endovascular interventions (Romiti et al., 2008; Varu et al., 2010).

Balloon angioplasty with and without stenting can be used to open narrowed or occluded vessels. In patients with longer lesions and more diffuse disease open surgical bypass techniques are typically used to provide revascularization to ischemic limbs (Gerhard-Herman et al., 2017; Hirsch et al., 2006; Norgren et al., 2007). In some cases, a hybrid approach is used with a combination of balloon angioplasty, stenting and surgical bypass. In cases where there are no revascularization options, patients may require a primary amputation of their limbs to manage pain and/or infection (Gerhard-Herman et al., 2017; Varu et al., 2010).

It is important to note that in Canada, and specifically in Calgary, revascularization is reserved with patients who have critical limb ischemia or severely life-limiting claudication. Many institutions do offer revascularization (typically endovascular) for patients who have IC. This is relevant given that patients with CLI have end-stage disease as noted previously, and typically have a significantly greater number of comorbidities.

Outcomes after revascularization

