Patency and limb salvage are the primary measures for revascularization success in CLI patients. Primary and secondary patency rates at one year are significantly lower with endovascular compared with open surgical techniques, while limb salvage rates are similar in both groups (Romiti et al., 2008). Table 2. shows results from a meta-analysis comparing endovascular versus open bypass outcomes in patients with CLI. While limb salvage rates are similar, this analysis does not capture the frequency of re-interventions for either modality. Conte et al. (2009) showed in a meta-analysis of infra-inguinal surgical bypass procedures that only 61% of patients remain free from any amputation or re-intervention at one year. That number is significantly higher in the endovascular group (Conte et al., 2009).

It is important to note that limb salvage rates always surpass patency rates regardless of treatment modality. This is because revascularization allows patients to heal ischemic wounds and hopefully increase ambulation which will assist with collateral vessel development.

Table 2. Meta-analysis of 1-month to 3-year patency, limb salvage, and patient survival (%) in patients with critical limb ischemia comparing percutaneous transluminal angioplasty vs bypass grafting

Result	1 month	6 months	1 year	2 years	3 years
Primary patency					
PTA	77.4 ± 4.1	65.0 ± 7.0	58.1 ± 4.6	51.3 ± 6.6	48.6 ± 8.0
Bypass	93.3 ± 1.1	85.8 ± 2.1	81.5 ± 2.0	76.8 ± 2.3	72.3 ± 2.7
P	<.05	<.05	<.05	<.05	<.05
Secondary patency					
PTA	83.3 ± 1.4	73.8 ± 7.1	68.2 ± 5.9	63.5 ± 8.1	62.9 ± 11.0
Bypass	94.9 ± 1.0	89.3 ± 1.6	85.9 ± 1.9	81.6 ± 2.3	76.7 ± 2.9
P	<.05	<.05	<.05		
Limb salvage					
PTA	93.4 ± 2.3	88.2 ± 4.4	86.0 ± 2.7	83.8 ± 3.3	82.4 ± 3.4
Bypass	95.1 ± 1.2	90.9 ± 1.9	88.5 ± 2.2	85.2 ± 2.5	82.3 ± 3.0
Patient survival					
PTA	98.3 ± 0.7	92.3 ± 5.5	87.0 ± 2.1	74.3 ± 3.7	68.4 ± 5.5
Bypass	NA	NA	NA	NA	NA

Exercise and Peripheral arterial disease

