- 2) Freedom from MALE
- 3) Target vessel and/or bypass patency
- 4) Survival at 1, 3 and 5 years

STUDY DESIGN

This study is a two phase, single-center, non-blinded randomized controlled trial. The first phase of the trial will include 20 patients; 10 assigned to post-operative exercise rehabilitation and 10 to best medical therapy. The primary objective of Phase I is to assess for feasibility and safety of this randomized controlled trial in CLI patients after revascularization. We will assess rate of enrollment, adherence to the exercise regimen and any unforeseen barriers or challenges that patients may encounter with the rehabilitation program.

If Phase I of the trial confirms that the exercise program is feasible and safe for CLI patients post-revascularization, we will proceed with Phase II of the trial. The primary objective for Phase II is to determine if a supervised exercise rehabilitation program will improve walking distance after revascularization compared with patients treated with best medical therapy. Phase II will also compare quality of life outcomes between the two groups.

STUDY POPULATION

The population to be studied in this group is patients with PAD and CLI Fontaine classification III and IV. This means that these patients will have ischemic rest pain in their legs and/or non-healing ischemic ulcers on their feet.

ENROLLMENT

Patients will be identified on a referral basis through our outpatient vascular surgery clinic. The seven practicing vascular surgeons in Calgary will be informed of the current study. Patients who have undergone revascularization for CLI will be identified for consideration of participation in this study within six months of their procedure. All surgical and ischemic wounds to be deemed sufficiently healed prior to assessment for fitness in the study. Once the attending vascular surgeon considers the patient fit to participate, the research coordinator will assess the patient for possible inclusion in the study.

Inclusion Criteria

- 1) Ambulating prior to procedure
- 2) Living independently prior to procedure
- 3) Available to attend all SEP and follow-up appointments
- 4) PAD Fontaine class III and IV (rest pain and tissue loss)
- 5) Entry with consent of vascular surgeon
- 6) Ischemia secondary to TASC A-D lesions identified on imaging (CTA or angiogram)
- 7) Able to understand and sign informed consent
- 8) >18 years of age

Exclusion Criteria

- 1) Confined to wheelchair

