Microsoft Excel will be used to generate a block randomization sequence for Phase I (20 patients) followed by a block randomization sequence for Phase II (44 patients) of the study. Patients who are eligible to participate in the study will be stratified by sex and randomized to either SEP or BMT. Block sizes of 4 and 6 will be used to prevent anticipation of the randomization sequence.

ALLOCATION CONCEALMENT

Once the random block sequence has been generated, allocation cards will be created and sealed in sequentially numbered opaque envelopes. The envelopes will be stored in a secured filing cabinet in the vascular surgery research office. The envelopes will be opened sequentially after a patient consents to participate in the study.

DATA COLLECTION

No study data will be collected until patients have reviewed and signed the informed consent. Opportunity to ask questions and have time independent from study team will be provided.

Data will be recorded using Excel spreadsheets. Medical outcomes and complications will be tracked using Vascubase software. Data will be stored on Alberta Health Services computers to maintain patient confidentiality.

STATISTICAL ANALYSIS

Normally distributed data will be presented as mean \pm SD. Results at baseline and 12 weeks will be compared using a paired t-test. For data that is not normally distributed, comparisons will be performed using a non-parametric Mann-Whitney test. Comparisons will be accepted as statistically significant at 95% confidence level ($p \leq 0.05$). STATA software will be used for statistical analysis.

ETHICAL CONSIDERATIONS

Patients who are randomized to the SEP group will be provided with tri-weekly visits for supervised exercise guidance and support. Patients will receive reimbursement for travel to and from the exercise facility. This will include refunds for gas, parking or other required transportation (taxi, public transport, etc).

FOLLOW UP OF PATIENTS WITHDRAWN FROM STUDY

Patients who withdraw or do not complete the program will be contacted and interviewed at the end of the 12 week study period to understand why they were unable to complete the training program.

LIMITATIONS

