One expected limitation of this study is the heterogeneity of the revascularization approach. Some patients will undergo endovascular treatment, while others will receive an open surgical bypass. Additionally, patients will not be stratified according to anatomical level of disease (aorto-iliac versus infrainguinal disease).

LONG-TERM FOLLOW-UP

This project is a pilot project with 12-week primary endpoint measures of functional capacity and quality of life. Given that we plan to extend to a broader randomized controlled clinical trial with long term follow-up, we will continue to follow the patients annually for five years. The annual follow-up will include QoL surveys, ABI measurements, ultrasound assessment for graft patency and any MALE. We will also monitor survival throughout this period.

REFERENCES

Adam, D. J., Beard, J. D., Cleveland, T., Bell, J., Bradbury, A. W., Forbes, J. F., . . . Storkey, H. (2005). Bypass versus angioplasty in severe ischaemia of the leg (BASIL): multicentre, randomised controlled trial. *Lancet*, 366(9501), 1925-1934. doi:10.1016/s0140-6736(05)67704-5

Agarwal, S. (2009). The association of active and passive smoking with peripheral arterial disease: results from NHANES 1999-2004. *Angiology*, 60(3), 335-345. doi:10.1177/0003319708330526

Badger, S. A., Soong, C. V., O'Donnell, M. E., Boreham, C. A., & McGuigan, K. E. (2007). Benefits of a supervised exercise program after lower limb bypass surgery. *Vasc Endovascular Surg*, 41(1), 27-32. doi:10.1177/1538574406296209

Bavry, A. A., Anderson, R. D., Gong, Y., Denardo, S. J., Cooper-Dehoff, R. M., Handberg, E. M., & Pepine, C. J. (2010). Outcomes Among hypertensive patients with concomitant peripheral and coronary artery disease: findings from the INternational VErapamil-SR/Trandolapril STudy. *Hypertension*, 55(1), 48-53. doi:10.1161/hypertensionaha.109.142240

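### Revascularisation approach is named as a limitation but not used in the analysis; a prespecified approach-stratified patency comparison would give a small gain at little cost

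*Combined protocol and SAP*

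**What the plan says.** The Limitations section states: "One expected limitation of this study is the heterogeneity of the revascularization approach". It goes on: "Some patients will undergo endovascular treatment, while others will receive an open surgical bypass". It adds that "patients will not be stratified according to anatomical level of disease". It proposes no way of handling either source of variation. The background section on revascularisation mentions a third category: "In some cases, a hybrid approach is used with a combination of balloon angioplasty, stenting and surgical bypass".

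Under Randomization, the only stratification factor is sex: "Patients who are eligible to participate in the study will be stratified by sex and randomized to either SEP or BMT". Under Statistical Analysis, the method for normally distributed data is: "Results at baseline and 12 weeks will be compared using a paired t-test". The alternative is a Mann-Whitney test. Neither takes a covariate, and no method is named for a binary outcome.

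Patency is a listed secondary outcome ("Target vessel and/or bypass patency"). It is assessed by duplex ultrasound at 2 and 12 weeks and then yearly for five years. On how approach relates to patency, the section on outcomes after revascularisation says: "Primary and secondary patency rates at one year are significantly lower with endovascular compared with open surgical techniques". Table 2 gives the figures.

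**The concern.** The plan identifies a factor that its own background links to one of its outcomes, calls it a limitation, and then makes no use of it. Adding strata to the randomisation of 64 patients is a real trade-off. Adjusting or stratifying an analysis by one two-level factor costs very little.

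Two things are at stake. In a particular small trial the arms may differ by chance in their share of endovascular procedures, and part of any patency difference would then reflect approach. Leaving a predictor out also gives up some precision. If the decision to adjust is left until unblinded data have been seen, it can be influenced by the result.

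**Working it through.** **Inputs.** Table 2 supplies patency and limb salvage by approach. The Sample Size section gives 64 patients, taken as 32 per arm. The documents do not give the share of endovascular procedures, so 50% is assumed, with 30 to 70% as the range.

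**Step 1: gap by approach (bypass minus PTA, percentage points).**

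| | 1 month | 6 months | 1 year | 2 years | 3 years |
|---|---|---|---|---|---|
| Primary patency, PTA | 77.4 | 65.0 | 58.1 | 51.3 | 48.6 |
| Primary patency, bypass | 93.3 | 85.8 | 81.5 | 76.8 | 72.3 |
| Primary gap | 15.9 | 20.8 | 23.4 | 25.5 | 23.7 |
| Secondary patency gap | 11.6 | 15.5 | 17.7 | 18.1 | 13.8 |
| Limb salvage gap | 1.7 | 2.7 | 2.5 | 1.4 | -0.1 |

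No scan is scheduled at 6 months. Linear interpolation to 12 weeks (84 days, 30.4 days per month) gives a weight of (84/30.4 - 1)/5 = 0.353, and a primary gap of 15.9 + 0.353 x (20.8 - 15.9) = 17.6 points. If the 12 weeks run from the first exercise session, the scan falls later and the gap moves towards 20.8.

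**Step 2: how often approach is imbalanced by chance.** With K endovascular patients among 64 and x of them in one arm of 32, the imbalance is |2x - K|/32. The exact hypergeometric probability of 20 points or more is 0.079 for K = 32 and 0.099 for shares of 30% or 70%. Treating the arms as two independent binomials gives 0.103 at 50% and 0.075 at 30% or 70%. Hence about 8 to 10%. In the 20-patient Phase I, the same imbalance arises in about 46 to 66% of trials, depending on share and method.

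**Step 3: the artefact from a 20-point imbalance.**

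- 12 weeks: 0.20 x 17.6 = 3.5 points
- 6 months: 0.20 x 20.8 = 4.2 points
- 1 year: 0.20 x 23.4 = 4.7 points

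**Step 4: set against sampling error.** At 6 months with a 50/50 mix, mean primary patency is (65.0 + 85.8)/2 = 75.4%. The standard error of the arm difference is sqrt(2 x 0.754 x 0.246/32) = 10.8 points, so the 95% half-width is about 21 points. The artefact is 4.2/10.8 = 0.39 standard errors, or 0.042 x 32 = 1.3 patients.

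**Step 5: precision lost for patency.** The variance explained by approach is (gap squared/4) divided by p(1 - p). At 6 months this is (0.208 squared/4)/(0.754 x 0.246) = 0.0108/0.1855 = 5.8%. The unadjusted interval is wider by 1/sqrt(1 - 0.058) - 1 = 3%. For secondary patency, approach explains 4.0%, about 2% of width.

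**Step 6: the 6-minute walk.** The documents give no effect of approach on walking distance, so the variance explained (R2) must be assumed. The stated 64 patients with 80% power at two-sided 0.05 imply a standardised difference of (1.96 + 0.84) x sqrt(2/32) = 0.70. No SD is given, so the 64 can be neither confirmed nor refuted; it does not bear on this point. Adjusted power is Phi(0.70 x sqrt(32/2)/sqrt(1 - R2) - 1.96):

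| Assumed R2 | 0.02 | 0.05 | 0.10 | 0.20 |
|---|---|---|---|---|
| Power | 80.8% | 82.0% | 84.0% | 87.9% |

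With a 50/50 mix, an R2 of 0.06 corresponds to a 0.5 SD difference in outcome between approaches, and 0.20 to a 1 SD difference.

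**The case against.** The best case for leaving the plan alone is that the harm is small. An unadjusted comparison of randomised arms already allows for chance imbalance in its error rate, and an artefact of 0.4 standard errors is well inside the noise. The trial calls itself a pilot and discloses the limitation. For walking distance the case for adjustment is weaker still. The first walk test follows the procedure and wound healing, and the outcome is change from that point, so any early effect of approach is already in the baseline. Limb salvage in Table 2 is nearly equal by approach, so a patency gap need not carry over to function. All of this stands, and it limits the point to a modest improvement. It does not make the improvement worthless, because prespecifying one stratified estimate costs almost nothing.

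Three stronger readings are tempting, and the documents do not support them.

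- *Approach shifts patency by about 20 points.* Table 2 shows an association. The titles in the reference list (one meta-analysis of infrapopliteal angioplasty, another of popliteal-to-distal vein bypass) suggest separate, non-randomised groups, whereas this trial also admits aorto-iliac disease. The figure of about 20 fits primary patency only.
- *An imbalance would pass for an effect of exercise.* Steps 3 and 4 show that it would be too small to do so by itself.
- *Adjustment needs no new data because approach is known for every patient.* The Measurements section does not list approach. The Intervention section randomises before the procedure, while the Enrollment section identifies patients after it. Under the former, the approach performed is a post-randomisation variable in an unblinded trial.

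**Conclusion.** The point holds as a minor one. The plan names approach as a limitation, has figures linking it to a listed secondary outcome, and does not use it. Randomisation protects against systematic bias. What remains is a patency interval about 3% wider than necessary and an unaddressed chance imbalance: 20 points or more in about 8 to 10% of 64-patient trials, with a 20-point imbalance worth 3.5 to 4.7 points between 12 weeks and one year.

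These sizes rest on a roughly even mix of approaches (30 to 70% for the imbalance), on Table 2 carrying over to this population, and on interpolation for the 12-week scan. Phase I is far more exposed to imbalance, but its stated purpose is feasibility and safety. A reader might infer a material loss of power for the primary outcome. The documents cannot show that, since every figure in step 6 depends on an assumed R2. Nor do they give figures for anatomical level, so the point is confined to approach.

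**What to change.** 1. Leave the randomisation unchanged.
2. Reconcile the Enrollment and Intervention sections on whether randomisation comes before or after the procedure. Record the planned approach before allocation as endovascular versus open or hybrid, and say how hybrids are coded. If randomisation turns out to follow the procedure, the approach performed is itself known before allocation and can serve.
3. As the main change, prespecify a between-arm patency estimate that is stratified by or adjusted for approach, and state which patency (primary or secondary) and which scan it uses. Results within each approach should be descriptive only, because the groups will be small.
4. Optionally, include planned approach with baseline distance and sex in a between-arm ANCOVA of 12-week 6MWT distance. The paired t-test must give way to such a model in any case, since it compares time points and cannot take a covariate.

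The cost is one recorded field, one degree of freedom in each model and a few sentences in the plan. The gain is modest: about 3% of interval width for patency, and an unknown amount for walking distance.
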